2.1.1 Full Analysis Set

The FAS will include all randomized patients. The FAS will be used for all efficacy analyses including patient-reported outcomes (PROs). Treatment groups will be compared on the basis of randomized study treatment, regardless of the treatment actually received. Patients who were randomized but did not subsequently receive study treatment are included in the analysis in the treatment group to which they were randomized.

2.1.2 PD-L1 TC \geq 1% Analysis Set

The PD-L1 TC \geq 1% analysis set will include the subset of patients in the FAS whose PD-L1 status is PD-L1 TC \geq 1% as defined by the Ventana SP263 PD-L1 immunohistochemistry (IHC) assay (i.e. 1% PD-L1– membrane expression in tumoral tissue) at randomization. Treatment groups will be presented based on the basis of the randomized study treatment.

2.1.3 Safety Analysis Set

The safety analysis set will consist of all randomized patients who received any amount of study treatment. Safety data will not be formally analyzed but summarized using the safety analysis set, according to the treatment received. If a patient receives any amount of durvalumab, they will be summarized in the durvalumab treatment group. If a patient only receives placebo, they will be summarized in the placebo treatment group.

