## 6 STUDY TREATMENTS

Study treatment is defined as any IP(s) (including marketed product comparator and placebo) or medical device(s) intended to be administered to a study participant according to the study protocol. Study treatment in this study refers to durvalumab (supplied as either double-blind or open-label) or placebo.

***Note for CSP v2.0: Placebo will no longer be administered to patients following implementation of this amendment at the study site.***

***From implementation of CSP v2.0 at site, preparation, storage, and administration of open-label durvalumab should occur as per durvalumab instructions in Sections 6.1, 6.3, and 6.4 (unless otherwise indicated in Section 10). Refer to Section 10 regarding the eligibility and duration of open-label durvalumab treatment, as well as required assessments during the treatment.***

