### **10.2.2 Patients in second screening or randomized and receiving study treatment**

At the time of CSP v2.0 implementation at site, Investigators and all randomized patients at that site will be unblinded to study treatment allocation. Patients in second screening (signed ICF2a but not yet randomized) who are deemed eligible and all patients currently receiving study treatment (regardless of treatment arm allocation) will have the option to receive open-label durvalumab (see Section 10.3.1).

For patients in second screening or currently receiving study treatment, there must be a visit **within 31 days of CSP v2.0 implementation at site** to discuss the option to start or continue open-label durvalumab. This visit can be performed on site or via telemedicine; the discussion between the patient and Investigator and its outcome must be recorded in the source documents. If this visit does not occur within 31 days of CSP v2.0 implementation at site, the patient will be considered lost to follow-up.

- For patients who do not choose to receive open-label treatment, or where Investigators deem this to be inappropriate, there must be a visit **within 31 days of CSP v2.0 implementation at site** to ensure all applicable data are collected and entered accurately into the study database. This visit may be performed on site or via telemedicine (and can coincide with the discussion indicated above) and must be recorded in the source documents. Once this final visit has been completed, the patient will then be discontinued from the study (see Section 10.2.1.3).
- For patients who choose to receive open-label durvalumab (and where Investigators deem this to be appropriate) they must sign the new ICF (ICF3) **within 31 days of CSP v2.0 implementation at site, and prior to receipt of open-label durvalumab.**

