#### 10.3.3 End of study definition

The end of the study is defined as when the last patient has received their last dose of durvalumab. Following implementation of CSP v2.0, the DCO will occur after the last patient has either discontinued the study or has signed consent (ICF3) to receive open-label durvalumab, whichever occurs later.

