3.3 Safety Variables

Safety and tolerability will be assessed in terms of AEs (including SAEs), deaths, laboratory data, vital signs, ECGs, and exposure. These will be collected for all patients. For physical examination, only information on whether the assessment was performed or not is recorded, and any abnormal findings are reported as either medical history or AEs.

Safety data will be summarized from the ‘On-treatment’ period, unless otherwise specified. ‘On-treatment’ is defined as assessments between the date/time of start of study treatment (i.e. durvalumab/placebo) and 90 days following discontinuation of study treatment (i.e. the last dose of durvalumab/placebo), or up to and including the date of initiation of the first subsequent anti-cancer therapy (including radiotherapy, except for palliative radiotherapy), whichever occurs first.

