4.2.6 Data Cut-Offs

Following implementation of CSP V2.0, the DCO will occur after the last patient has either discontinued the study or has signed consent (ICF3) to receive open-label durvalumab, whichever occurs later. This will be followed by DBL and the primary DFS analysis. The study will then be concluded.

Details regarding the approach used for removing post-DCO data from SAS datasets can be found in the AstraZeneca Oncology Guidance on Data Cut-off Processing and Clean file/DBL Considerations document as well as the DCO Specifications for this study.

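### The SAP's on-treatment safety window has no cut at the switch to open-label durvalumab, so a serious event on open-label drug can be counted as a placebo event

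*SAP*

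**What the plan says.** **The switch.** Protocol 10.2.2 states that, once v2.0 is implemented at a site, "all patients currently receiving study treatment (regardless of treatment arm allocation) will have the option to receive open-label durvalumab". Protocol Section 6 adds: "Placebo will no longer be administered to patients following implementation of this amendment at the study site". A visit to discuss the option has a fixed limit: "If this visit does not occur within 31 days of CSP v2.0 implementation at site, the patient will be considered lost to follow-up". The open-label consent (ICF3) has the same 31-day limit.

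**The data cut-off (DCO).** Protocol 10.3.3: "the DCO will occur after the last patient has either discontinued the study or has signed consent (ICF3) to receive open-label durvalumab". SAP 4.2.6 uses the same trigger, ending "or has signed consent (ICF3) to receive open-label durvalumab, whichever occurs later".

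**The safety rules.**
- SAP 2.1.3, like Protocol 9.3.3, sets the group by actual treatment: "If a patient receives any amount of durvalumab, they will be summarized in the durvalumab treatment group". No period is specified.
- SAP 3.3 ends the on-treatment period at "90 days following discontinuation of study treatment (i.e. the last dose of durvalumab/placebo"), or at the first subsequent anti-cancer therapy if that comes sooner.
- SAP 4.2.9.1 applies the same two limits to the AE summaries and to the split of fatal SAEs in the deaths table.
- SAP 3.3.2 and 4.2.12 define exposure with no open-label cut. For patients still on treatment at the analysis, exposure runs to the DCO.

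**What counts as study treatment.** Protocol Section 6: "Study treatment in this study refers to durvalumab (supplied as either double-blind or open-label) or placebo". SAP 3.3.1 names only durvalumab and placebo and is silent on open-label supply. SAP 1.2 mentions the open-label option as design background. SAP Section 6 names only the visit-response table as a change from the protocol.

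**What is recorded after ICF3.** According to the amendment summary (row for Section 6.3), dosing goes to source documents and not to the eCRF; Protocol 6.3 itself names source documents. Protocol 10.1 stops study assessments apart from SAE and pregnancy reporting, and Protocol 10.3.2 limits reporting to SAEs.

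**The concern.** Safety of durvalumab against placebo is the only secondary objective (SAP 1.1.2). A placebo patient who starts open-label durvalumab changes treatment inside the 90-day follow-up of the last placebo dose, and nothing in the SAP closes the placebo window at that moment. An SAE that begins on durvalumab can then appear in the placebo column as an on-treatment event. The deaths table would likewise class a fatal one as starting before subsequent therapy.

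The error would run in a known direction: events on durvalumab counted against placebo make the comparison look more favourable to durvalumab. With about 30 randomized patients (SAP 1.2), one misplaced event is visible in a percentage. The AE listing fields named in SAP 4.2.9.1 include the onset date but not the switch date, so a reader could not separate such events from those fields alone.

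**Working it through.** The plan gives no figure to reproduce. The check is on the text, followed by illustrative arithmetic.

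**1. Can a placebo patient be on open-label durvalumab before the DCO?** Yes. The amendment is implemented site by site, and the 31-day limit runs from each site's own date. The DCO waits for the last patient in the study. A patient at an early site can sign, be dosed and still be before the DCO.

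**2. Which post-switch data can reach the safety tables?**
- Doses: probably none. They go to source documents, while SAP 3.3.2 identifies delays and interruptions from the Exposure eCRF form.
- Non-serious AEs and study laboratory data: not expected, because assessments stop and only SAEs are reported.
- SAEs: open. Protocol 8.4.1 puts all SAEs in the CRF. The note at the head of Protocol Section 8 keeps Sections 8.3 and 8.4 in force for the time before open-label treatment starts. The two do not settle whether a later SAE enters the study database.

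**3. Where is such an SAE counted?** With no open-label dose in the data, the patient stays in the placebo group and the last recorded dose is placebo. The window stays open for 90 days unless subsequent anti-cancer therapy starts. The SAP does not class open-label durvalumab as such therapy, so the SAE falls in the placebo on-treatment period. Deaths are tabulated by treatment group in the full analysis set, so the death count by arm does not move; only the onset split is affected.

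**4. How much of the window can overlap?** Let g be the days from last placebo dose to first open-label dose, and D the days from last placebo dose to the DCO.

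Share = max(0, min(90, D) − g) / 90

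Neither g nor D is documented. Case 1 assumes the last placebo dose on implementation day and the next dose on the 4-weekly schedule (g = 28). Case 2 assumes the last placebo dose 28 days before implementation and the first open-label dose 31 days after it (g = 28 + 31 = 59). The ±3-day dosing windows are ignored.

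| Case | D | Share of 90-day window |
|---|---|---|
| 1 (g = 28) | 31 | 3/90 = 3.3% |
| 1 | 60 | 32/90 = 35.6% |
| 1 | 90 or more | 62/90 = 68.9% |
| 2 (g = 59) | 59 | 0/90 = 0% |
| 2 | 75 | 16/90 = 17.8% |
| 2 | 90 or more | 31/90 = 34.4% |

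These are shares of person-time, not of events.

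**5. Weight of one patient.** With 15 per arm, 1/15 = 6.7 points; with an arm of 18, 1/18 = 5.6; with an arm of 12, 1/12 = 8.3. The weight applies to a category only if the patient had no earlier event in it.

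**6. The secondary reading.** If open-label doses were in the data and counted as study treatment, SAP 2.1.3 would regroup each switched patient together with the blinded placebo period. From 15/15, one switch gives 16 durvalumab and 14 placebo; five give 20 and 10. As an invented example, suppose five switchers each had one AE on blinded placebo and nobody else had any. Then 5/15 (33.3%) on placebo against 0/15 becomes 5/20 (25.0%) on durvalumab against 0/10.

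**The case against.** **A reader might infer that placebo patients' blinded AEs, laboratory data and exposure will be moved to the durvalumab group.** The wording of SAP 2.1.3, read with the definition in Protocol Section 6, permits this. The documents do not support it as the likely result, because dosing after ICF3 is kept out of the eCRF and the rule would have no dosing record to act on. This part of the objection stands, and regrouping is therefore only a secondary issue.

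**Open-label durvalumab could be read as subsequent anti-cancer therapy, which would already close the window.** SAP 3.3.1 does not mention open-label supply, and SAP 1.2 sets current study treatment apart from the open-label option. But nowhere does the SAP state this reading, and Protocol Section 6 points the other way by counting open-label supply as study treatment. The ambiguity remains.

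**The remaining route needs many things to coincide.** A placebo patient must still be on treatment at implementation, although most patients are expected to be discontinued from the study (Protocol 10.2). The patient must then choose to switch, be dosed before the DCO and have an SAE within 90 days of the last placebo dose, and that SAE must reach the database. This stands and limits the size.

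**Data-cut handling is partly deferred to documents not available here.** SAP 4.2.6 refers to DCO specifications, which may bear on what stays in the database. They concern data after the DCO, whereas the gap lies before it, so they do not clearly close it.

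**The consequence is limited.** All outputs are descriptive, AEs are listed with onset dates, and about 30 patients can be reviewed individually. This stands as to severity, but individual review still needs the switch date.

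**Conclusion.** The concern holds as a minor gap. SAP v2.0 was written for Protocol v2.0 but left the on-treatment window and the deaths-table split as if no patient would change treatment. An SAE on open-label durvalumab, before the DCO and in the database, can be tabulated under placebo. The 2.1.3 grouping rule needs the same clarification but is unlikely to misplace data in practice.

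The number of affected patients is undocumented and may be zero. One patient is about 6.7 points of an arm's percentage, assuming an even split of 30. In the cases computed, the overlap runs from 0% to about 69% of the 90-day window, depending on assumed switch and DCO dates; the upper figure is not a forecast. No hypothesis test or error rate is involved. DFS is summarized by randomized arm and is unaffected. Patients who start open-label durvalumab from second screening were never randomized and lie outside the safety set.

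**What to change.** - **SAP 2.1.3:** set the safety group by the treatment received in the double-blind period.
- **SAP 3.3, 3.3.2, 4.2.9.1 and 4.2.12:** in both arms, limit safety and exposure summaries to the double-blind period. End it at the first open-label dose (the ICF3 date if the dose date is unavailable) or at the existing window end, whichever is earlier. In the deaths table, keep the total and apply the same end date to the onset split.
- **Listings:** list open-label SAEs from both arms separately, with the switch date.
- **SAP Section 6:** record the departure from Protocol 9.3.3.

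Applying the cut to both arms matters. Cutting only placebo patients would leave open-label SAEs in the tables for one arm and remove them from the other.

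The cost is wording in these sections and one date per patient who goes open-label. ICF3 dates must already be known, because they help set the DCO. The downside is that open-label SAEs appear in a listing and not in the summary tables, and the SAP departs from the protocol's grouping rule. DFS censoring does not change.

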2.2 Protocol Deviations

The following general categories will be considered important protocol deviations (IPDs) and will be listed and discussed in the CSR as appropriate:

- Inclusion criteria deviations: Patients who deviate from inclusion criteria 2, 6, 11 and/or 13 per Section 5.1 of the CSP.
- Exclusion criteria deviations: Patients who deviate from exclusion criteria 4 and/or 13 per Section 5.2 of the CSP.
- Discontinuation criteria for study product met but patient not withdrawn from study treatment.
- Investigational product (IP) deviation:
 - (a) Patient received incorrect IP to that to which they were randomized.
 - (b) Patients who were randomized but did not receive IP.
- Excluded medications taken: Received prohibited concomitant systemic anti-cancer therapy.
- Deviations related to study procedure: Baseline RECIST scan > 49 days before randomization.

Patients who receive the wrong treatment at any time will be included in the safety analysis set as described in Section 2.1. During the study, decisions on how to handle errors in treatment dispensing (with regard to continuation/discontinuation of study treatment or, if applicable, analytically) will be made on an individual basis with written instruction from the study team leader and/or statistician.

The IPDs will be listed and summarized by randomized treatment group. IP deviation of patients who were randomized but did not receive IP will lead to exclusion from the safety analysis set. None of the other deviations will lead to patients being excluded from the analysis sets described in Section 2.1. A per-protocol analysis excluding patients with specific IPDs is not planned.

The programmatic determination of the IPDs above will be a separate process outlined in the study Protocol Deviations Plan, which will also include full details regarding IPDs as well as the activities and responsibilities related to the IPD process.

In addition, other study deviations captured from the eCRF module for inclusion/exclusion criteria will be tabulated and listed. Any other deviations from monitoring notes or reports may be reported in an appendix to the CSR.

3. PRIMARY AND SECONDARY VARIABLES

3.1 Derivation of RECIST Visit Responses

For this adjuvant study, where patients with no evidence of disease at baseline (as assessed by CT/magnetic resonance imaging [MRI]) will be entered in the study, the definition of new lesions (NLs) in RECIST 1.1 is used for the assessment of disease recurrence.

For all patients, the RECIST tumour response data will be used to determine each patient's visit response according to RECIST version 1.1. It will also be used to determine if and when a patient has progressed in accordance with RECIST.

Baseline radiological tumour assessments are to be performed no more than 28 days + 7 days prior to randomization and ideally as close as possible to the date of randomization. Tumour assessments are then performed every 8 weeks \pm 1 week following randomization until week 48, and then every 12 weeks \pm 1 week until unequivocal disease recurrence or primary DFS analysis. Upon detection of disease recurrence, an additional follow-up scan should be performed 4 to 8 weeks later and evaluated using post-progression radiological criteria.

If an unscheduled assessment is performed, and the patient has not had disease recurrence, every attempt should be made to perform the subsequent assessments according to the original

imaging visit schedule (relative to the date of randomization). If a dose delay of study treatment (i.e. durvalumab/placebo) occurs, RECIST scans should continue according to the original imaging visit schedule. This schedule is to be followed in order to minimise any unintentional bias caused by some patients being assessed at a different frequency than other patients.

3.1.1 New Lesions – Site Investigator Data

At each post-baseline visit, the Investigator should record an overall assessment based on the presence or absence of unequivocal NLs. This section provides the definitions of the criteria used to determine and record overall response at the investigational site at each visit.

Details of any NLs will be recorded with the date of assessment. The presence of one or more unequivocal NLs is assessed as progression and will indicate disease recurrence.

A lesion identified at a follow up assessment as local/regional, distant, or second primary NSCLC is considered a NL and will indicate disease recurrence. The development of a new cancer other than NSCLC should be regarded as an SAE.

The finding of a NL should be unequivocal: i.e. not attributable to differences in scanning technique, change in imaging modality or findings thought to represent something other than tumor. If a NL is equivocal, for example, because of its small size, the treatment and tumor assessments should be continued until the previously (pre-existing) NL has been assessed as unequivocal at a follow-up visit. If repeat scans (4 to 8 weeks later) definitively confirm there is a NL, then recurrence should be declared using the date of the initial post-baseline scan where the equivocal NL was first identified, without an intervening period of lesion absence.

Both equivocal and unequivocal NLs will be recorded in the eCRF. Unequivocal NLs will be identified via a Yes/No tick box on the new unequivocal lesions (post-randomization) eCRF form. If the question ‘Any unequivocal new lesions since baseline’ has not been answered with Yes or No and the NL details are blank this is not evidence that no unequivocal NLs are present, but should not overtly affect the derivation. This scenario (i.e. whereby NL response is NE) should only occur in exceptional cases, as missing data for the NL field should always be queried.

3.1.2 Overall Visit Response – Site Investigator Data

[Table 2](#) defines how NL information will be used to determine an overall visit response.

Table 2 Overall Visit Responses

Target lesions	Non-target lesions	New lesions	Overall visit response
NA	NA	NE	NE
NA	NA	No	NED
NA	NA	Equivocal	NED*
NA	NA	Yes	PD

* Disease recurrence (i.e. PD) may be backdated to a timepoint where an equivocal NL was identified, under specific conditions outlined in section 3.1 and 3.2.1.

NA Not applicable; NE Not evaluable; NED No Evidence of Diseases (only relevant if there were neither target lesions nor non-target lesions at baseline); PD Progressive disease.

3.2 Efficacy Variables

3.2.1 Disease-Free Survival (DFS)

Disease-free survival as assessed by the Investigator is the primary endpoint in this study and is defined as the time from the date of randomization until any one of the following events below, whichever occurs first, regardless of whether the patient withdraws from randomized therapy or receives another anti-cancer therapy prior to disease recurrence (i.e., date of DFS event or censoring – date of randomization + 1 day):

- Date of disease recurrence using Investigator assessments according to RECIST 1.1
 - Local, regional, or distant disease recurrence
 - Diagnosis of a second primary NSCLC
- Date of death from any cause

Disease recurrence should be based on the finding of an unequivocal NL. However, if a NL is initially equivocal (i.e. where an equivocal lesion converts to unequivocal), then the progression date should be backdated to the post-baseline follow-up scan when the NL first appeared without an intervening period of lesion absence. If equivocal lesions are present at baseline, they will not be documented on the baseline eCRF.

Patients who have not experienced disease recurrence and are alive at the time of DCO will be censored at the latest date of assessment from their last evaluable RECIST 1.1 assessment.

However, if the patient experiences disease recurrence or dies after 2 or more missed visits, the patient will be censored at the latest evaluable RECIST 1.1 assessment prior to the 2 missed visits (note: an NE visit is not considered a missed visit). Given the scheduled visit assessment scheme (i.e. every 8 weeks \pm 1 week after randomization for the first 48 weeks, then every 12 weeks \pm 1 week thereafter until appearance of disease recurrence or until

primary DFS analysis) the definition of 2 missed visits will change. The definitions are shown in [Table 3](#).

Table 3 Definition of Two Missed Visits

Previous RECIST assessment	Two missed visits (duration)	Explanation
Study day < 274 (week 39)	18 weeks	$2 \times 8 \text{ weeks} + 1 \text{ week for an early assessment} + 1 \text{ week for a late assessment} = 18 \text{ weeks.}$
Study day 274 to < 344 (>week 39 to < week 49)	22 weeks	Over this period, the scheduled frequency of RECIST assessments changes from q8w to q12w. Take the average of 8 and 12 weeks which gives 10 weeks. $2 \times 10 \text{ weeks} + 1 \text{ week for an early assessment} + 1 \text{ week for a late assessment} = 22 \text{ weeks.}$
Study day 344 onwards (week 49)	26 weeks	$2 \times 12 \text{ weeks} + 1 \text{ week for an early assessment} + 1 \text{ week for a late assessment} = 26 \text{ weeks.}$

RECIST Response Evaluation Criteria in Solid Tumours; q8w Every 8 weeks; q12w Every 12 weeks.

If the patient has no evaluable assessments or does not have baseline data, they will be censored at day 1 unless they die within 2 visits of baseline (i.e. 17 weeks [$2 \times 8 \text{ weeks} + 1 \text{ week for a late assessment}$]), then they will be treated as an event with the date of death as the event date. Additionally, patients with unequivocal evidence of disease at baseline (as assessed by the Investigator) will be censored at randomization (day 1).

The primary endpoint analysis of DFS on the FAS analysis set will be based on Investigator assessments according to RECIST 1.1. The DFS time will always be derived based on scan/assessment dates and not visit dates.

RECIST 1.1 assessments/scans contributing toward a particular visit may be performed on different dates. The following rules will be applied:

- For Investigator assessments, the date of disease recurrence will be determined based on the earliest of the RECIST assessment/scan dates of the component that indicates disease recurrence.
- When censoring a patient for DFS, the patient will be censored at the latest of the scan dates contributing to a particular overall visit assessment.

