Efficacy assessments of the primary endpoint of DFS will be derived using Investigator assessments according to RECIST 1.1 and pre-specified definitions of disease recurrence (ie, local or regional recurrence, distant recurrence, second primary NSCLC) and by survival assessments. All randomized patients and patients in the observation arm will be followed for disease recurrence until the primary DFS analysis and followed for safety and survival until the completion of the study. Disease evaluations utilize images from CT (preferred) or MRI, each preferably with IV contrast, of the chest and abdomen (including liver and adrenal glands) collected during screening/baseline and at selected timepoints during the study duration. Any other areas of disease involvement should be additionally imaged based on the signs and symptoms of individual patients

An IDMC comprised of independent experts will meet approximately 12 months after the first patient has been dosed with IP or after approximately 50 patients have received at least 1 dose of IP (whichever occurs first) to assess the safety and tolerability of durvalumab, and will report back to the Sponsor. The timing of subsequent reviews will be determined by the IDMC but will not occur more frequently than every 6 months. Full details of the IDMC procedures will be specified within the IDMC Charter. The IDMC safety reviews will be conducted in an unblinded manner. Scientific rationale for study design

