#### **8.1.1.1 Evidence of disease recurrence**

Disease recurrence is defined as evidence of RECIST 1.1-defined disease recurrence on CT or MRI scan and/or pathological disease on biopsy by investigational site assessment

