### **Distant recurrence**

Distant recurrence is defined as spread of disease beyond the area of the tumor bed, hilum or mediastinal lymph nodes and can describe extrathoracic disease, metastasis to the contralateral lung, pleural metastasis, pleural effusion, or pericardial effusion. Distant recurrence should be diagnosed by radiological examination and/or histopathological confirmation when the metastatic lesion is easily accessible for biopsy.

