#### **9.4.1.2 Primary endpoint: disease-free survival**

DFS is defined as the time from the date of randomization until the date of disease recurrence (local, regional, or distant disease recurrence or second primary NSCLC) using Investigator assessments according to RECIST 1.1, or date of death due to any cause, whichever occurs first.

Patients who are disease-free, ie, have not experienced disease recurrence, and alive at the time of analysis will be censored at the latest date of assessment from their last evaluable RECIST 1.1 assessment. However, if the patient experiences disease recurrence or dies after 2 or more missed visits, the patient will be censored at the latest evaluable RECIST 1.1 assessment prior to the 2 missed visits. If the patient has no evaluable assessments or does not have baseline data, they will be censored at Day 1 unless they die within 2 visits of baseline, then they will be treated as an event with the date of death as the event date. The primary endpoint analysis of DFS will be based on Investigator RECIST 1.1 assessments.

The DFS time will always be based on scan/assessment dates and not visit dates.

DFS rate at 6 and 12 months is defined as the proportion of patients alive and disease-free at 6 and 12 months respectively, estimated from Kaplan-Meier plots of the primary endpoint of DFS.

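### Does the SAP's DFS derivation wrongly leave out recurrence proven by biopsy?

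*SAP*

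**What the plan says.** **Protocol, collection and design sections.** Section 8.1.1.1 defines recurrence as evidence of "RECIST 1.1-defined disease recurrence on CT or MRI scan and/or pathological disease on biopsy by investigational site assessment". Its text on distant disease reads: "Distant recurrence should be diagnosed by radiological examination and/or histopathological confirmation when the metastatic lesion is easily accessible for biopsy". Section 4.1 states that DFS is "derived using Investigator assessments according to RECIST 1.1 and pre-specified definitions of disease recurrence".

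**Protocol, endpoint and RECIST sections.** Section 9.4.1.2 defines the primary endpoint by recurrence "using Investigator assessments according to RECIST 1.1, or date of death due to any cause, whichever occurs first". Section 9.4.1.1 and Table 7 likewise tie DFS to investigator RECIST 1.1 assessments. Appendix G opens by sending the reader to the RECIST new-lesion definition when judging recurrence. Its paragraph on histology and cytology keeps biopsy histology and effusion cytology out of the RECIST assessment. Its paragraph on clinical examination requires CT or MRI for lesions found that way.

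**SAP.** Section 3.1 says the new-lesion definition "in RECIST 1.1 is used for the assessment of disease recurrence". Section 3.1.1 adds: "A lesion identified at a follow up assessment as local/regional, distant, or second primary NSCLC is considered a NL and will indicate disease recurrence". Table 2 returns progression only when the new-lesion answer is Yes. Section 3.2.1 states: "Disease recurrence should be based on the finding of an unequivocal NL". On dating it says "the date of disease recurrence will be determined based on the earliest of the RECIST assessment/scan dates of the component that indicates disease recurrence". Biopsy is not mentioned in these rules.

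**The concern.** The and/or in protocol 8.1.1.1 appears to make biopsy sufficient on its own. The SAP reduces recurrence to one imaging-style field and one scan-based date. A patient with proven disease on biopsy and no new lesion ticked would have visits coded as no evidence of disease. If alive at data cut-off, that patient would be censored at the last evaluable scan. Two sites or two programmers could handle the same patient differently.

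This would bear on the primary output, because SAP 4.2.2.1 reports events and censorings with reasons and adds Kaplan-Meier curves. SAP Section 1 also promises that changes to protocol specifications appear in SAP Section 6, and Section 6 lists only the visit-response table. If the imaging-only rule is a departure from the protocol, it has not been declared.

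**Working it through.** No figure in the plan depends on this point, so the check is mainly a reading of the passages together.

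**Step 1: which protocol text defines the endpoint?** Table 7, 9.4.1.1 and 9.4.1.2 name investigator RECIST 1.1 assessments. Appendix G says recurrence is judged by new lesions and that histology plays no part in the RECIST assessment. The SAP's rule in 3.1 repeats the Appendix G instruction, and SAP 3.2.1 tracks 9.4.1.2. SAP Section 6 is framed as changes from the planned analyses in protocol version 2. Against Section 9 of the protocol, nothing has changed here. The conflict is between 8.1.1.1 and the protocol's own 9.4.1.2 and Appendix G.

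**Step 2: which biopsied patients are affected?**

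| Situation | Result under the SAP |
|---|---|
| Lesion on scan, then biopsied | Event, dated to the scan. Protocol 8.1.1.2 gives the same date. |
| Equivocal lesion on scan, biopsy shows tumor | The investigator can call it unequivocal. SAP 3.1.1 contrasts unequivocal with findings believed not to be tumor, a question that tissue can settle. The date goes back to the scan on which the lesion first appeared. |
| Biopsy first, scan positive later | Event. Only the date differs. |
| Biopsy positive, scans never positive, patient dies | Event at death, subject to the two-missed-visits rule. |
| Biopsy positive, no unequivocal new lesion, alive at data cut-off | Censored if no new lesion is recorded. |

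Only the last row can change event status through the biopsy rule itself. The notes to protocol 8.1.1.1 require complete restaging at first documented recurrence and a further scan 4 to 8 weeks later, so few patients should reach that row.

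**Step 3: size per patient.** SAP 1.2 expects about 30 randomized patients, allocated 1:1. An even split is assumed, giving 30 / 2 = 15 per arm.

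- Pooled FAS: 1 / 30 = 3.3 percentage points.
- One arm of 15: 1 / 15 = 6.7 points.
- Uneven split of 17 and 13: 1 / 17 = 5.9 points and 1 / 13 = 7.7 points.

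These figures are what any single recoded patient would produce in a study this small. They do not estimate an expected error, because the number affected is not given and may be zero.

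**The case for a change.** The best opposing case is that 8.1.1.1 is explicit. Section 4.1 also pairs RECIST with the pre-specified recurrence definitions, so biopsy belongs to the endpoint. Section 8.1 is kept under protocol version 2.0 for reference and data completion, so it still describes how recurrence was recorded. Section 8.1.1.2 even allows dating from a palpable lesion once tumor is established, which the SAP's scan-based dates do not cover. The safety net is thinner near version 2.0 implementation: study assessments then stop (10.1), and no study imaging follows discontinuation (10.2.1.3). A recurrence found first by biopsy at that time might never get its confirming scan.

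Part of this stands. The protocol does disagree with itself, and the SAP adopts the RECIST reading without saying so. SAP 3.1.1 does not state whether biopsy alone makes a lesion unequivocal.

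It does not show that the SAP rule is wrong. Either of two opposite rules would answer the complaint, provided one was written down. Making biopsy alone an event would bring histology into an endpoint defined by RECIST 1.1, against Appendix G. It would also need a new date convention and a data field that neither document shows to exist. An imaging-only statement would restate what the SAP already does.

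**Conclusion.** The concern identifies a real inconsistency in the protocol's wording, but the SAP needs no change. Its new-lesion rule matches the endpoint as defined in protocol 9.4.1.2 and Appendix G, so the charge of an undeclared departure is overstated. Analysts who follow the SAP as written obtain a sound investigator-assessed RECIST DFS. SAP 3.1.1 leaves room for the investigator to record a lesion identified at follow-up as a new lesion.

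The residual case is narrow, and no patient in it is documented. One would shift the pooled event percentage by 3.3 points, or an arm's by 5.9 to 7.7 points across the splits shown. No test, power or type I error depends on it, since protocol 10.4 and SAP Section 4 make every analysis descriptive. SAP 4.2.2.1 also lists all collected RECIST data, reports reasons for censoring and tabulates first subsequent therapy relative to recurrence. A patient treated for recurrence while coded as disease-free would therefore have a good chance of being noticed.

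This conclusion assumes about 30 randomized patients, sites that restage as the protocol requires, and no unusual cluster of biopsy-only recurrences just before implementation. The eCRF was not available, so how sites could enter such a case is unknown.
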